9.1.2. Institutional Review Board (IRB)/Ethics Committee (EC) Approval

This protocol and any accompanying material to be provided to the patient (such as advertisements, patient information sheets, or descriptions of the study used to obtain informed consent) will be reviewed and approved by the governing IRB/EC of the participating center prior to study initiation. Approval from the IRB/EC should be documented in a letter to the Investigator specifying the protocol number, protocol version, documents reviewed, and date on which the committee met and granted the approval.

Any modifications or amendment to documents originally submitted for review must also be submitted to the IRB/EC for approval prior to implementation. Additionally, the IRB/EC must be informed of any serious or unexpected AEs, new information that may adversely affect the safety of the patients or the conduct of the study, annual updates and/or requests for re-approval, and when the study has been completed.

9.1.3. Informed Consent

It is the responsibility of the Investigator or designee to obtain written informed consent from each individual participating in this study after adequate explanation of the aims, methods, objectives, and potential hazards of the study and prior to undertaking any study-related procedures. The Investigator, or designee, must utilize an IRB-approved consent form for documenting written informed consent. Each informed consent will be appropriately signed and dated by the patient

and the person obtaining consent. A copy of the signed consent form will be provided to the patient and the original will be maintained with the patient's records.

9.1.4. Conflicts of Interest

The Investigator will be paid by the Sponsor of this study for study-related expenses, but will not profit from results, whether positive or negative, with regard to the product being evaluated. The Investigator will disclose any financial conflicts of interest to the Sponsor, should they arise, as required in 21 CFR part 54.

9.1.5. Confidentiality

The Investigator must assure that patients' anonymity will be strictly maintained and that their identities are protected from unauthorized parties. Only patient initials and an identification code (i.e., not names) should be recorded on any form submitted to the sponsor and IRB. The Investigator must keep a patient log showing codes, names, and addresses for all patients screened and for all patients enrolled in the trial.

9.1.6. Study Files and Retention of Records

The Investigator must maintain adequate and accurate records to enable the conduct of the study to be fully documented and the study data to be subsequently verified. These documents should be classified into 2 separate categories (although not limited to) the following (1) Investigator's study file, and (2) patient clinical source documents.

The Investigator's study file will contain the protocol/amendments, eCRF and query forms, IRB/EC approval with correspondence, informed consent, drug records, staff curriculum vitae and authorization forms, and other appropriate documents and correspondence.

Patient clinical source documents can include (although is not limited to) the following: patient hospital/clinic records, physician's and nurse's notes, appointment book, original laboratory reports, electrocardiogram (ECG), electroencephalogram (EEG), X-ray, pathology and special assessment reports, consultant letters, screening and enrollment log, etc.

All clinical study documents must be retained by the Investigator until at least two years after the last approval of a marketing application in an International Conference on Harmonization (ICH) region (i.e., United States, Europe, or Japan) and until there are no pending or contemplated marketing applications in an ICH region; or, until two years after the IND is discontinued and regulatory authorities have been notified. The Investigator must notify the Sponsor prior to destroying any clinical study records.

Should the Investigator wish to move study records to another location, arrangements must be made to store these in sealed containers so that they can be returned sealed to the Investigator in case of a regulatory audit. Where source documents are required for the continued care of the patient, appropriate copies should be made for storage outside of the site.

9.1.7. Case Report Forms

For each patient who receives study drug, an eCRF must be completed and signed by the principal Investigator or sub-Investigator within a reasonable time period after data collection. This also applies to records for those patients who fail to complete the study. If a patient withdraws from the study, the reason must be noted on the eCRF. If a patient is withdrawn from the study because

of a treatment-limiting adverse event, thorough efforts should be made to clearly document the outcome.

9.1.8. Drug Accountability

The Investigator, or designee (i.e., pharmacist), is responsible for ensuring adequate accountability of all used and unused study drug. This includes acknowledgment of receipt of each shipment of study product (quantity and condition), inventory at the site, distribution to, collection from, use by patient, and the destruction or return of unused study medication to the Sponsor. Dispensing records will document quantities received and quantities dispensed to patients, including lot number, date dispensed, patient identifier number, patient initials, and the initials of the person dispensing the medication. The Investigator will assure that the study medication and records described in this section will be stored in a locked cabinet suitable for storage of pharmaceutical products and in accordance with the conditions specified in the Investigator's Brochure. Investigators must also assure that study medication and records will be available for examination by the study monitor during periodic visits.

During the study, the investigator will be notified of any expiry dates or retest date extensions of study drug supplies. If an expiry date notification is received during the study, the site must complete all instructions outlined in the notification, including segregation of expired clinical study material for destruction or return to the Sponsor or its designee.

At study initiation, the monitor will evaluate the site's standard operating procedure for study drug disposal/destruction in order to ensure that it complies with study requirements. Accountability records and inventory will be inspected during periodic visits throughout the study. Drug reconciliation may also be performed by a monitor during periodic visits, and the site may return used drug kits after reconciliation has been completed. At the Study Termination Visit, following final drug reconciliation by the monitor, the study site will be instructed by the Sponsor or its designee to return all unused study drug supplies, including empty containers.

9.1.9. Inspections

The Investigator will provide access to source documents and all study records for this trial to appropriately qualified personnel from the Sponsor, or its representatives, and to regulatory authority inspectors.

9.2. Sponsor Responsibilities

9.2.1. Study Materials and Instructions

It is the sponsor's responsibility to ensure that the Investigator is provided with the documents and other study materials necessary to conduct the study. Examples of those materials include, but are not limited to: protocol, Investigator's Brochure, study drug, eCRF, SAE collection forms, logs, etc. The sponsor will also provide training and oversight through site and medical monitoring.

9.2.2. Protocol Modifications

Protocol modifications, except those intended to reduce immediate risk to study patients, will be made by Sponsor-initiated amendment. IRB/EC approval must be obtained before changes can be implemented.

9.3. Joint Investigator/Sponsor Responsibilities

9.3.1. Access to Information for Monitoring

In accordance with International Conference on Harmonization Good Clinical Practice (ICH E6 (R2)) guidelines, study monitors must have direct access to the Investigator's source documentation in order to verify the data recorded in the eCRFs for consistency.

The monitors, both central and field monitors, are responsible for routine review of the eCRFs at regular intervals throughout the study, to verify adherence to the protocol, and the completeness, consistency and accuracy of the data being entered on them. The monitors should have access to any patient records needed to verify the entries on the eCRFs. The Investigator agrees to cooperate with the monitors to ensure that any problems detected in the course of these monitoring activities are resolved.

9.3.2. Study Discontinuation

Both the sponsor and the Investigator reserve the right to terminate the study at any time. Should this be necessary, both parties will arrange discontinuation procedures and notify the appropriate regulatory authority(ies) and IRBs/ECs. In terminating the study, the Sponsor and the Investigator will assure that adequate consideration is given to the protection of the patients' interests.

APPENDIX 1. TIME AND EVENTS SCHEDULES

Event	TIME AND EVENTS SCHEDULE FOR THE STUDY						
	Screening	Baseline ^a	Treatment		Follow-ups		
	Visit 1	Visit 2	Visit 3	Visits 4 & 5	Visits 6+		
Event	Day -28 to 1	Baseline Day 1	Week 2 (\pm 2 day)	Months 1 & 2 (\pm 3 days)	In Clinic at Month 4 and Every 4 Months thereafter until Study Termination Visit ^b (\pm 7 days)	Phone Visits at Month 6 and Every 4 Months thereafter until Study Termination Visit ^b (\pm 3 days)	Study Termination Visit ^c
Informed Consent	X						
Confirmation of eligibility	X	X					
Medical History & Demographics	X						
Physical Examination ^d	X	X		X ^e	X ^f		X ^c
Weight/Height Measurement	X	X ^g			X ^f		X
Vital Signs ^h	X	X	X	X	X ^f		X
Clinical Labs (blood) ⁱ	X	X	X	X	X ^f		X
NT-proBNP (blood) ⁱ	X	X	X	X	X		X
Serum Pregnancy Test for Females ^j	X						
Urine Pregnancy Test for Females ^j		X					
Infectious Disease Screen	X						
6MWT & Functional Class	X	X	X	X	X		X
Pulmonary Function Testing	X						
Inhalation Device User Survey ^k		X	X		X ^f		X
MLWHF questionnaire		X		X ^e	X ^f		X
Patient DPI Training ^l		X	X	X	X		
Record Last Dose of Inhaled Treprostinil		X	X	X	X		X
LIQ861 Administration ^m		X	X	X	X		
Treatment-Emergent Adverse Events ⁿ		X	X	X	X	X	X
Prior Medication Assessment	X	X					
Concomitant Medications		X	X	X	X	X	X
Assess PAH Symptoms		X	X	X	X	X	X
Consider and Record Dose Adjustments			X	X	X	X	
Collect Unused Study Drug			X	X	X		X
Dispense Study Drug			X	X	X ^o		
Schedule Next Visit	X	X	X	X	X ^o	X	

a. This table is for assessments for all subjects not participation in the PK Sub-Study. For Day 1 and Day 2 assessments in the PK Sub-Study see the PK Sub-Study T&E Table (below).

b. Patients will continue on 4-month periodic follow-up visits from the completion of Visit 6 until the Study Termination Visit.

c. Study Termination Visit should be completed within 1 month of drug approval or study termination or when a patient is discontinued from the study.

- d. A full PE will be conducted at Visit 1, at Visit 6 and every 12 months thereafter, and at Study Termination; a brief PE will be conducted during Visit 2 & Visit 5.
- e. Assessment is to be conducted at Visit 5 (Month 2) only.
- f. Assessment is to be conducted at Visit 6 and every 12 months thereafter.
- g. Height does not need to be assessed at Visit 2.
- h. Vital signs, temperature, blood pressure, respiratory rate, and heart rate (blood pressure, respiratory rate, and heart rate will be measured after the patient has been upright and rested for at least 5 minutes).
- i. Obtain venous blood for clinical laboratory tests before study drug administration.
- j. Females of childbearing potential only.
- k. The Inhalation Device User Survey should only be administered to Tyvaso Transition patients.
- l. Patients should receive device training prior to the first dose of LIQ861. Patients should be retrained at each remaining visit until the Study Termination Visit.
- m. Refer to instructions for use. For Tyvaso transition patients at Baseline, and all patients at post-Baseline visits, time of LIQ861 administration should be at least 4 hours after the last dose of inhaled treprostinil (Tyvaso or LIQ861).
- n. Only treatment-emergent AEs will be collected.
- o. The next Phone Visit and In Clinic Follow-up Visit should both be scheduled before the end of an in-clinic visit. During Phone Visits, the timing of the following In Clinic Follow-up visit should be confirmed.

Event	TIME AND EVENTS SCHEDULE FOR THE PK SUB-STUDY											
	Screening		Baseline ^a				Treatment				Treatment through Follow-Up	
	Visit 1		Visit 2				Visit 2				Visits 3+	
Event	Day -28 to 0						Day 1 (Starting Hour)					
	-1	0	1	2	3	4	-1	0	1	2	3	4
Informed Consent		X										
Confirmation of eligibility		X										
Medical History & Demographics		X										
Physical Examination ^b		X										
Weight/Height Measurement ^c		X										
Vital Signs ^d		X										
Clinical Labs (blood) ^e		X					X ^f					
NT-proBNP		X					X					
Serum Pregnancy Test for Females ^g		X					X					
Urine Pregnancy Test for Females ^g		X					X					
Infectious Disease Screen		X					X					
6MWT & Functional Class		X					X					
Pulmonary Function Testing		X					X					
Inhalation Device User Survey ^h							X					
MLWHF questionnaire							X					
Patient DPI Training ⁱ							X					
Record Last Dose of Inhaled Treprostинil							X					
Tyvaso Administration							X					
LIQ861 Administration							X					
Plasma for Pharmacokinetics ^j							X					
Treatment-Emergent Adverse Events ^k							X					
Prior Medication Assessment		X					X					
Concomitant Medications							X					
Assess PAH Symptoms							X					
Dispense Study Drug							X					
Schedule Next Visit		X					X					

Proceed to Visit 3 in
Main Study T&E Table
([above](#))

- This table is for assessments in the PK Sub-Study. For Day 1 assessments for patients that are not in the PK Sub-Study, see the Study T&E Table ([above](#))
- A full PE will be conducted on Visit 1; a brief PE will be conducted during Visit 2.
- Height does not need to be assessed at Visit 2.
- Vital signs, temperature, blood pressure, respiratory rate, and heart rate (blood pressure, respiratory rate, and heart rate will be measured after the patient has been upright and rested for at least 5 minutes).
- Obtain venous blood for clinical laboratory tests at predose and 4 hours post-dose on Day 1 and Day 2.
- Blood for clinical labs and PK collected in the 4th hour after dosing should be obtained prior to administration of the first dose of LIQ861 on Day 1 and prior to administration of the second dose of LIQ861 on Day 2.
- Females of childbearing potential only.
- The Inhalation Device User Survey should be administered after administration of LIQ861.
- Patients should receive device training prior to the first dose of LIQ861 on Day 1 and Day 2. Timing in relation to dose administration is not critical.

- j. For PK sub-study only: Collect blood for measurement of treprostinil concentrations predose (within 30 minutes before dosing), and at 5, 10, 15, 20, 25, 30, 45, 60, 90, 120, and 180 minutes and 4 hours after study drug administration. Record actual times of blood collection for each timepoint.
- k. Adverse events will be collected after administration of Tyvaso.

APPENDIX 2. GUIDANCE FOR LIQ861 DOSE SELECTION AND TITRATION

Dose Titration

Titration to a higher dose of treprostinil in LIQ861 should be governed by patient's degree of symptomatic relief, not to tolerance of PGI₂ side effects. If there are no symptoms of PGI₂ excess, doses of LIQ861 may be increased in 25 µg treprostinil strength increments according to the following guidelines up to the Maximum Allowed Dose of 150 µg treprostinil strength.

Dosing in excess of 150 µg treprostinil strength has not been previously studied and should not be implemented without consent from the sponsor.

Selection of Initial Dose in LIQ861 Add-on Patients

Start the patient on LIQ861 QID at the 25 µg treprostinil capsule strength.

1. After initial administration of LIQ861, supervise the patient's condition for a minimum post-dose observation period of 1 hour and discharge at the discretion of the Investigator.
2. Patients should be called between Day 5 and Day 7 post-dose to assess symptomatic relief and tolerance of LIQ861 therapy and a decision should be made whether to maintain the patient at the same dose or to increase to 50 µg LIQ861, administered as a single capsule QID.
3. At the Week 2 Visit, or after 2 weeks of stable LIQ861 QID administration, if the patient is experiencing sufficient symptomatic relief AND is tolerating the treatment, that dose should be maintained unless symptoms worsen.
 - a. If the patient is not experiencing sufficient symptomatic relief OR is not tolerating the treatment, LIQ861 may be increased or decreased by 25 µg treprostinil strength increments, respectively.
4. Additional dosing increases may be implemented at 25 µg increments per week, however dose escalations are limited to a maximum of 150 µg as dosing in excess of 150 µg treprostinil strength has not been previously studied and should not be implemented without consent of the Sponsor. Prior to any dose titration the Investigator should contact the patient by phone to assess degree of symptomatic relief and tolerance and need/desire to adjust the LIQ861 dose.

Selection of Initial Dose in Tyvaso Transition Patients

If the patient is transitioning from Tyvaso, determine the appropriate LIQ861 starting dose from [Table 2](#) below:

Table 2. Starting LIQ861 dose based upon Tyvaso Dose

Tyvaso Dose ¹		Starting LIQ861 Dose
Estimated Treprostinil	Breaths of Tyvaso	Capsule Strength
≤ 30 µg	≤ 5	25 µg
≥ 36 µg and ≤ 48 µg	≥ 6 and ≤ 8	50 µg
≥ 54 µg and ≤ 66 µg	≥ 9 and ≤ 11	75 µg
≥ 72 µg and ≤ 84 µg	≥ 12 and ≤ 14	100 µg
≥ 90 µg and ≤ 102 µg	≥ 15 and ≤ 17	125 µg
≥ 108 µg	≥ 18	150 µg

¹Tyvaso doses up to 54 µg are consistent with the label. However, it is understood that physicians may choose to dose in excess of 54 µg and it is important to explore transitioning these patients given that LIQ861 was well tolerated up to 150 µg in healthy volunteers.

After initial administration of LIQ861 on Day 1, supervise the patient's condition for a minimum post-dose observation period of 4 hours.

For the second and third dose on Day 1, titrate LIQ861 dose in increments of 25 µg treprostinil strength based on clinical observations, patient feedback, and Investigator discretion. The patient should be observed for a minimum of 1 hour after the second dose of LIQ861 and may be discharged at the discretion of the Investigator.

At the Week 2 Visit, or after 2 weeks of QID administration of LIQ861, if the patient is experiencing sufficient symptomatic relief AND is tolerating the treatment, that dose should be maintained unless symptoms worsen.

- If the patient is not experiencing sufficient symptomatic relief OR is not tolerating the treatment, LIQ861 may be increased or decreased by 25 µg treprostinil strength increments, respectively.

Additional dosing increases may be implemented at 25 µg increments per week, however dose escalations are limited to a maximum of 150 µg, unless agreed to by the Sponsor. Prior to any dose titration the Investigator should contact the patient by phone to assess degree of symptomatic relief and tolerance and need/desire to adjust the LIQ861 dose.

Tyvaso Transition Patients – PK Sub-Study Procedures

If the patient is transitioning from Tyvaso and is enrolled in the PK Sub-Study, the patient's final dose of Tyvaso on Day 1 of the study, and the starting dose for LIQ861 should be administered as described in [Table 3](#). In the event that a patient's prescribed Tyvaso dose is not a multiple of 3 breaths, the dose administered on Day 1 for PK assessments will be selected as described in [Table 3](#).

Table 3. Tyvaso and LIQ861 Dosing for Patients in the PK Sub-Study

Prescribed Tyvaso Dose ¹		PK Sub-Study Dosing	
Estimated Treprostinil	Breaths of Tyvaso	Day 1: Breaths of Tyvaso	Day 2: LIQ861 Capsule
≤ 30 µg	≤ 5	3	25 µg
≥ 36 µg and ≤ 48 µg	≥ 6 and ≤ 8	6	50 µg
≥ 54 µg and ≤ 66 µg	≥ 9 and ≤ 11	9	75 µg
≥ 72 µg and ≤ 84 µg	≥ 12 and ≤ 14	12	100 µg
≥ 90 µg and ≤ 102 µg	≥ 15 and ≤ 17	15	125 µg
≥ 108 µg	≥ 18	18	150 µg

¹Prescribed Tyvaso Dose is the dose on which the patient has been stable in concordance with the study eligibility criteria.

Day 1

1. PK samplings will be collected over a 4 hour period after administration of the final Tyvaso dose. LIQ861 should be administered at the appropriate starting dose beginning with the second dose on Day 1.
 - a. If the starting dose of LIQ861 is not tolerated, the next dose of LIQ861 may be decreased by 25 µg treprostinil strength.
 - b. If the starting dose does not appear to be providing similar efficacy to the patient's Tyvaso treatment, the next dose of LIQ861 may be increased by 25 µg and the patient should be observed for at least an hour after the increase prior to discharge from the clinic at the Investigator's discretion.

Day 2

1. For the first dose on Day 2, LIQ861 should be administered at the same dose as the last tolerated dose taken on Day 1, and PK samples should be collected over a 4 hour period. After completion of the PK sampling, the patient may be discharged at the discretion of the Investigator.
2. At the Week 2 Visit, or after 2 weeks of QID administration of LIQ861, if the patient is experiencing sufficient symptomatic relief AND is tolerating the treatment, that dose should be maintained unless symptoms worsen.
 - b. If the patient is not experiencing sufficient symptomatic relief OR is not tolerating the treatment, LIQ861 may be increased or decreased by 25 µg treprostinil strength increments, respectively.
3. Additional dosing increases may be implemented at 25 µg increments per week up to a maximum of 150 µg. Prior to any dose titration the Investigator should contact the patient by

phone to assess degree of symptomatic relief and tolerance and need/desire to adjust the LIQ861 dose.

Management of Side Effects

If symptoms of PGI₂ excess are observed, further dose increases of LIQ861 should be avoided until these symptoms subside.

If side effects cannot be tolerated or medically managed, one or more of the following strategies may be employed:

- Reduction of LIQ861 in 25 µg treprostinil strength increments until symptoms subside
- Discontinuation of LIQ861

Employment of any of the above strategies for mitigation of non-tolerated side effects should be documented in the eCRFs.

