Scheduled study visits to the clinic will occur at Screening, Baseline (Day 1), Week 2, Month 1, Month 2, Month 4, and every 4 months thereafter (e.g., Month 8, Month 12, etc.) until study termination or regulatory approval. During this time, dose titration may be ordered at the Investigator’s discretion and in accordance with the Guidance for LIQ861 Dose Selection and Titration ([Appendix 2](#)).

Telephone contact to assess adverse events (AEs), concomitant medications, and PAH symptoms will be made every 4 months beginning at Month 6 (e.g., Month 6, Month 10, etc.) until the Study Termination Visit. Telephone contact is not necessary during months in which a study visit is scheduled. The Study Termination Visit will occur after regulatory approval of LIQ861 or after the Sponsor decides to terminate the development program.

Patients that clinically worsen on open-label LIQ861, as determined by Investigator's discretion may be withdrawn from the study and rescue therapy initiated per standard of care.

Sub-Study - Comparative Bioavailability Assessment

At least 18 PAH patients on Tyvaso (stable doses QID for at least 3 months) will be included in a comparative bioavailability sub-study ("PK sub-study") comparing treprostinil exposure in a one-directional crossover design that utilizes the patient's prescribed Tyvaso dose as the comparator to LIQ861.

The dose titration schedule for these patients is described in [Appendix 2](#).

Patients participating in this sub-study will have a trough level PK blood sample collected prior to self-administering their Tyvaso dose at the Investigational site at Baseline (morning dose Day 1), under the supervision of study staff. Following administration of Tyvaso, blood will be collected for PK analysis of treprostinil through 4 hours post-dose and the patients will remain in the clinic for safety observations per Investigator discretion. After the 4 hour post-dose blood draw, the patients will be transitioned to LIQ861 for subsequent doses of treprostinil in accordance with their typical dosing regimen. If the initial LIQ861 dose (based on the instructions in [Appendix 2](#)) is tolerated, patients will take two more doses of LIQ861, 4 hours apart, during Day 1. If the initial LIQ861 dose is not tolerated, dose adjustments may be made as needed during the next two doses taken on Day 1.

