5.3. Selection of Doses in the Study

The results of study LTI-101 showed that the observed exposures of treprostinil after inhalation of LIQ861 are proportional to administered dose levels consistent with the capsule strengths selected for this study. Mean Cmax and AUCinf values from the LTI-101 study were compared with mean exposure levels reported in published literature and in the Drug Approval Reviews from the FDA. Commonalities between the exposures observed in the LTI-101 study and those reported for Tyvaso were used to project a Tyvaso Approximate Dose (TAD) for LIQ861. This assessment was the basis of the original dose selection guidance (LTI-301 Protocol Amendment 1, 13-Nov-2017).

Review of interim PK data from crossover patients in LTI-301 has shown that the initial TAD for LIQ861 may be providing lower plasma exposure than originally projected. The estimated treprostinil doses delivered from Tyvaso appear to result in plasma exposures that are more consistent with the estimated emitted doses from LIQ861. The trend of observed plasma exposures from within-patient PK comparisons in interim LTI-301 data review, combined with estimates of expected emitted doses from LIQ861 administration, are the basis of revised initial transition dose selection guidance provided in [Table 2](#) and the directed dose administrations for future PK patients provided in [Table 3](#) (see [Appendix 2](#)).

If the patient is not already on Tyvaso, the starting dose will be LIQ861 QID at the 25 µg treprostinil capsule strength. For patients transitioning from Tyvaso, patients should start at doses recommended in the Guidance for LIQ861 Dose Selection and Titration, [Appendix 2](#). For all patients, dosing may be titrated per instructions provided in [Appendix 2](#).

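### Appendix 2 gives two rules for the Day 2 LIQ861 dose in the PK sub-study, and they disagree when the last tolerated Day 1 dose is not the starting dose

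*Protocol*

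**What the plan says.** **Day 2 LIQ861.** Table 3 in Protocol Appendix 2 has a column headed "Day 2: LIQ861 Capsule". It gives 25, 50, 75, 100, 125 or 150 µg according to the prescribed Tyvaso band, and neither the column nor the footnote makes an exception for Day 1 adjustment. Section 5.3 refers to "the directed dose administrations for future PK patients provided in" Table 3. The sentence introducing the table, however, describes its LIQ861 dose as the starting dose, and the Day 1 step places that dose second on Day 1. The Day 2 step of the same appendix says "LIQ861 should be administered at the same dose as the last tolerated dose taken on Day 1". The synopsis and Section 3.1 give the same rule as the Day 2 step.

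**Day 1 LIQ861.** Section 3.1 says: "If the initial LIQ861 dose is not tolerated, dose adjustments may be made as needed during the next two doses taken on Day 1". Appendix 2 step 1a allows a 25 µg decrease for intolerance. Step 1b adds that if efficacy does not appear similar to Tyvaso, "the next dose of LIQ861 may be increased by" 25 µg.

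**Day 1 Tyvaso.** The synopsis and Section 3.1 describe the patient's "prescribed Tyvaso dose as the comparator to LIQ861", and Section 3.1 has samples drawn "prior to self-administering their Tyvaso dose at the Investigational site at Baseline (morning dose Day 1"). Neither mentions rounding. Appendix 2 says that when the prescribed dose is not a multiple of 3 breaths, "the dose administered on Day 1 for PK assessments will be selected as described in" Table 3, which gives 3, 6, 9, 12, 15 or 18 breaths.

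**Analysis.** Section 8.6 defines Frel as the AUCinf ratio multiplied by the inverse dose ratio. It does not say whether each dose is the prescribed, tabulated or administered one. SAP Section 4.3 refers to the protocol and a separate PK SAP for PK details and says the PK data have already been reported.

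**The concern.** A dosing table and the numbered step beneath it should not give different doses for the same administration. Here they can. A site working from the column heading gives the strength for the patient's band. A site working from the Day 2 step gives whatever was last tolerated on Day 1. Two like patients, both adjusted on Day 1, could therefore receive different Day 2 doses while each site believes it is following the protocol.

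Two things are at stake. The first is safety: after a Day 1 decrease for intolerance, the table leads back to the dose that was not tolerated. The second is the secondary objective, comparative bioavailability. The Day 2 administration supplies the whole LIQ861 profile, so the reader of the PK report needs to know which rule produced it.

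**Working it through.** **Step 1. Reproduce Table 3's own conversion.** Dividing estimated treprostinil by breaths at each stated bound gives 30/5, 36/6, 48/8, 54/9, 66/11, 72/12, 84/14, 90/15, 102/17 and 108/18. All equal 6 µg per breath, so the table is internally consistent. The problem is how the table relates to the text.

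**Step 2. Find when the two Day 2 rules differ.** Let S be the Table 3 strength, which is also the Day 1 starting dose, and L the last dose tolerated on Day 1. The column heading gives S on Day 2 and the text gives L.

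- Starting dose kept: L = S, and the rules agree.
- Decreased by 25 µg for intolerance, lower dose tolerated: L = S − 25, and the rules differ.
- Increased by 25 µg, higher dose tolerated: L = S + 25, and the rules differ.
- Increased by 25 µg, not tolerated: if the starting dose was tolerated and is the last such dose, L = S and the rules agree.

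**Step 3. Size of the gap.** For one step, gap = 25/S.

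| Table 3 dose S (µg) | L after one decrease | Gap | L after one increase | Gap |
|---|---|---|---|---|
| 25 | no lower strength | not applicable | 50 | 100% |
| 50 | 25 | 50% | 75 | 50% |
| 75 | 50 | 33% | 100 | 33% |
| 100 | 75 | 25% | 125 | 25% |
| 125 | 100 | 20% | 150 | 20% |
| 150 | 125 | 17% | above 150, only if the Sponsor agrees | not counted |

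The 100% figure arises only from an increase, so it says nothing about intolerance. The range relevant to intolerance is 17% to 50%.

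**Step 4. Secondary wording mismatch, Day 1 Tyvaso.** At 6 µg per breath, Table 3 equals the prescribed dose at 3, 6, 9, 12, 15 and 18 breaths. Elsewhere it departs from it:

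- 5 breaths: 18 against 30 µg, (18 − 30)/30 = −40%.
- 8 breaths: 36 against 48 µg, −25%.
- 17 breaths: 90 against 102 µg, −12%.
- 20 breaths: 108 against 120 µg, −10%, because the table stops at 18 breaths.

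The general description of the comparator in the synopsis and Section 3.1 is therefore inexact for these patients.

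**Step 5. Frel.** If each AUCinf is paired with the dose that produced it, the dose term is correct under either Day 2 rule. Comparing patients dosed under different rules then relies on dose-proportional exposure, which Section 1.3 reports for single LIQ861 doses of 25 to 150 µg in healthy volunteers.

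**The case against.** The strongest reply is that only one column heading is out of line. The synopsis, Section 3.1 and the Appendix 2 Day 2 step agree with one another, the introducing sentence speaks of a starting dose, and Section 5.3 does not mention Day 2. To go wrong, a site would have to overlook the first instruction under the Day 2 heading, just below the table. That is fair, and it limits how often the conflict would have mattered. It does not remove it: both instructions are in Appendix 2, so preferring the specific over the general settles nothing, and Section 5.3 gives the table the status of directed dosing.

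Three stronger readings are tempting, and the documents do not support them.

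- *The Day 1 Tyvaso dose is equally contradictory.* Appendix 2 sends the final Tyvaso dose to Table 3 and states the rule for doses that are not a multiple of 3 breaths. The synopsis and Section 3.1 are loose summaries, not a competing instruction.
- *Section 3.1 forbids a Day 1 increase.* It mentions adjustment for intolerance and is silent on efficacy. It bases the initial dose on Appendix 2 and refers there for titration, where step 1b adds the increase.
- *Frel is inflated.* That needs an analyst to divide an AUC by a dose that was not given. The ordinary reading of the formula is the dose behind each AUC, and the PK SAP, which is not among these documents, may define it.

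**Conclusion.** The contradiction over the Day 2 LIQ861 dose is real and lies inside Appendix 2. It affects only patients whose last tolerated Day 1 dose differed from the starting dose. For them, one 25 µg step separates the two rules by 17% to 50% of the Table 3 dose after a decrease and by 20% to 100% after an increase. These figures assume a single step and no dose above 150 µg. The documents do not give the number of patients adjusted on Day 1 or the rule that sites followed, so no effect on the reported bioavailability result can be computed or claimed.

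The Day 1 Tyvaso and Day 1 adjustment mismatches are secondary matters of wording, and the undefined dose in Frel is a gap in detail. No hypothesis test is planned, and SAP Section 3.3 reports enrolment as a completed count (121 subjects). With the PK data already reported, the remaining effect is on how that report is read.

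**What to change.** 1. Reconcile the Table 3 column heading, its introducing sentence, Section 5.3, Section 3.1, the synopsis and the Appendix 2 Day 2 step, so that each PK day has one dosing rule. In the same pass, align the descriptions of the Tyvaso comparator and of Day 1 LIQ861 adjustment. Which rule applies is for those with clinical responsibility; this review does not choose.
2. As a supporting clarification, state in Section 8.6 that Frel uses the doses actually administered on Day 1 (Tyvaso) and Day 2 (LIQ861). If the PK SAP already says so, a cross-reference is enough.
3. With the PK results, list the patients whose administered doses differed from Table 3, so that the reader can see how many were affected and in which direction.

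The cost is wording and one listing, with no new samples. The listing assumes that administered doses were recorded. Section 6.2.3 asks for the time of the last inhaled treprostinil dose but does not list a breath count, so this should be checked. New wording cannot change dosing already given; its use is to make the reported comparison readable.
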